8.3 Sample Size

We intend to accrual a maximum of 38 subjects for this study. Because the efficacy of eltrombopag in this patient population is unknown, we would like to reject the treatment as quickly as possible with a small number of patients if the treatment is not effective. We will use the Two-Stage Minimax Design outlined in Table 1 of Simon ⁽¹⁾ with a response probability of 20% or less to terminate the treatment and the hypothesized actual response probability of 40% or more. The sample size is determined by testing the null hypothesis $H_0: p \leq 20\%$ versus the alternative $H_1: p \geq 40\%$ at a significance level of 0.05 and a power of 0.8. At the first stage, 18 subjects will be accrued and the trial will be terminated by accepting the null hypothesis if 4 or fewer subjects respond to the treatment within 16 to 20 weeks. If 5 or more subjects respond to the treatment within 16 weeks at the first stage, then an additional 15 subjects will be accrued at the second stage. If needed, the replacement of 5 drop-out subjects will bring the total number of subjects to $n=38$. The null hypothesis of $p \leq 20\%$ will be accepted (i.e., the drug will be rejected) if the total number of responders within 16 to 20 weeks is 10 or less. This sample size is calculated by the PASS power analysis and sample size software (NCSS, LLC., [name]).

Subjects who discontinue the study drug prematurely (before 16 weeks):

Platelet count measurement will be attempted even if a patient discontinues study drug. Patients who withdraw from the study for reasons other than lack of efficacy or toxicity (rendering platelet count missing) may be replaced. All other patients should be evaluable for efficacy. Based on the assumed drop-out rate of 15-20% and the goal of having 33 evaluable patients, 5 additional patients may be enrolled if needed.

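### Section 8.3 words the stage-1 futility rule on 18 subjects accrued rather than 18 evaluable; if drop-outs are not replaced before that look, the chance of stopping an effective drug rises from 9% to about 21–27%

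*Combined protocol and SAP*

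**What the plan says.** Everything relevant is in section 8.3 (Sample Size) of the combined protocol and SAP.

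- **Design.** "We will use the Two-Stage Minimax Design outlined in Table 1 of Simon", with a null response rate of 20%, an alternative of 40%, and the test "at a significance level of 0.05 and a power of 0.8".
- **Stage 1.** "At the first stage, 18 subjects will be accrued and the trial will be terminated by accepting the null hypothesis if 4 or fewer"; the count is of responders.
- **Stage 2.** With 5 or more responders, "then an additional 15 subjects will be accrued at the second stage". The drug is rejected if the total number of responders is 10 or fewer.
- **Replacement.** Up to five drop-outs may be replaced, for a maximum of 38 subjects. Patients who withdraw for reasons other than lack of efficacy or toxicity may be replaced; all others are to be evaluable for efficacy.
- **Drop-out.** The assumed rate is 15–20%, and the section then sets "the goal of having 33 evaluable patients, 5 additional patients may be enrolled if needed".

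The word *evaluable* is attached to the total of 33 and never to the 18. The replacement provision is permissive, names no stage and gives no timing.

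**The concern.** A Simon two-stage boundary is calibrated to a fixed number of outcomes at each look. The cut of 4 belongs to 18 known outcomes. If it is applied to 18 enrolled subjects of whom about three have no outcome, four or fewer responses become much more likely even when the drug works.

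The section opens by using accrual for the maximum of 38, a number that includes replaced drop-outs. On that usage, 18 accrued means 18 enrolled, whether or not an outcome was obtained. A team following the sentence literally would take the look on fewer than 18 outcomes, while the final decision would rest on an evaluable total. At stake is the trial's only formal efficacy go/no-go decision and its stated power of 0.8.

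**Working it through.** **Inputs, all from 8.3.** p0 = 0.20; p1 = 0.40; n1 = 18 with r1 = 4; n2 = 15, so N = 33 with r = 10; drop-out d = 15–20%; at most 38 enrolled.

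**Formulas.** With m outcomes at stage 1 and n2 at stage 2:

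- P(stop at stage 1) = P[Bin(m, p) ≤ 4]
- P(declare effective) = Σ over x = 5,…,m of P[Bin(m, p) = x] × P[Bin(n2, p) ≥ 11 − x]

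**Step 1: the plan's own design.** With m = 18 and n2 = 15, P(stop | 0.40) = 0.0942, power = 0.8011 and type I error = 0.0458. An exhaustive search for the minimax design at these error rates returns 4/18 and 10/33, so the stated design reproduces.

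**Step 2: outcomes lost at stage 1, topped up later to 33 evaluable (n2 = 33 − m).**

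| Outcomes at stage 1 | P(stop, p = 0.40) | Ratio to design | Power | Type I error |
|---|---|---|---|---|
| 18 | 0.094 | 1.0 | 0.801 | 0.046 |
| 17 | 0.126 | 1.3 | 0.782 | 0.043 |
| 16 | 0.167 | 1.8 | 0.755 | 0.040 |
| 15 | 0.217 | 2.3 | 0.718 | 0.036 |
| 14 | 0.279 | 3.0 | 0.669 | 0.031 |

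Expected stage-1 outcomes are 18 × 0.85 = 15.3 at 15% drop-out and 18 × 0.80 = 14.4 at 20%.

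**Step 3: random drop-out, m ~ Bin(18, 1 − d), averaging over m.** The stopping probability equals P[Bin(18, 0.40 × (1 − d)) ≤ 4].

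- d = 15%: P[Bin(18, 0.34) ≤ 4] = 0.213; power 0.717; type I error 0.037.
- d = 20%: P[Bin(18, 0.32) ≤ 4] = 0.269; power 0.672; type I error 0.033.

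**Step 4: the cap of 38.** Step 3 assumes that 33 evaluable are always reached. But 38 × 0.85 = 32.3 and 38 × 0.80 = 30.4, both below 33. Reaching 33 on average needs 33/0.85 = 38.8 (39 enrolled) or 33/0.80 = 41.25 (42 enrolled). With 18 enrolled at stage 1, up to 20 at stage 2, and never more than 33 evaluable, the results are in the middle column. The last column enrols until 18 subjects are evaluable, takes the look, then continues within the 38.

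| Drop-out | Power, no replacement before the look, cap 38 | Power, replacement before the look, cap 38 |
|---|---|---|
| 15% | 0.690 | 0.757 |
| 20% | 0.612 | 0.694 |

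With replacement before the look, P(stop | 0.40) returns to 0.094. Power stays below 0.80 only because five replacements are too few at these drop-out rates.

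**The case against.** The strongest reply is that the text does not commit to the unfavourable reading. The same verb is used for both stages, and 18 + 15 = 33 is the number that the section calls evaluable, so *accrued* may simply name the design sample size. The paragraph on premature discontinuation applies to any subject, so replacement before the look is permitted. The final rule does not use the word *evaluable* either, and nowhere is a stage-1 drop-out said to count as a non-responder. This stands. A reader might infer that the plan as written stops an effective drug two to three times as often as designed, but the documents do not support that as a flat statement. It follows only if drop-outs are left unreplaced at the look.

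Nor is there an arithmetic error in the design: the boundaries and error rates reproduce exactly.

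A second reply is that the 40% could be the rate among all accrued subjects, with drop-outs counted as failures; stage 1 would then behave as designed. Section 8.3 does not rule this out, but replacing drop-outs to reach an evaluable total fits better with a rate among evaluable subjects.

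Third, partial replacement shrinks the effect. One unreplaced stage-1 drop-out gives stopping 12.6% and power 78.2%. That is right, although power is already below the stated 0.8.

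Finally, the notes in sections 5.1 and 11.1 that no enrolled subject required sachets are in the past tense. Enrolment may therefore be advanced and the look already taken. That changes the form of the remedy, not the point.

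**Conclusion.** The point holds conditionally. Section 8.3 does not say whether its stage-1 termination rule applies to 18 enrolled or 18 evaluable subjects, or whether drop-outs are replaced first. On the evaluable reading, stage 1 stops an effective drug with probability 9.4%, as designed. On the literal reading at 15–20% drop-out, that probability is about 21–27%. Power is then about 72–67% if 33 evaluable are eventually reached, and about 69–61% under the plan's own cap. Type I error falls in the literal scenario, so the cost falls on an effective drug.

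Assumptions: drop-outs are the replaceable withdrawals with no outcome; loss is independent of response; the 40% applies to evaluable subjects; and the full 15–20% are lost in this way. Subjects who leave for toxicity or lack of efficacy remain evaluable under 8.3, so the effect is smaller if the 15–20% includes them.

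A reader might also infer that power can be restated as 67–72%, or that correcting the stage-1 wording restores 80%. Neither follows at the assumed drop-out. The first ignores the cap of 38, and the second fails because 38 enrolled do not on average yield 33 evaluable.

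**What to change.** In 8.3, replace the stage-1 wording with: *The first-stage decision is made on the first 18 evaluable subjects. A first-stage subject who qualifies for replacement is replaced before the decision, within the maximum of 38 enrolled.* Word stage 2 the same way, as 15 further evaluable subjects.

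In the same place, state that at the assumed drop-out and the cap of 38 the power is about 76% (15%) or 69% (20%), rather than 80%. Do not insert 67–72%.

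If the stage-1 look has already been taken, record how many of the 18 had an outcome and whether any had been replaced.

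The cost is two or three sentences and a short wait. Reaching 18 evaluable takes on average 18/0.85 − 18 = 3.2 extra subjects at 15% drop-out, or 18/0.80 − 18 = 4.5 at 20%, drawn from the five replacements already allowed. At 20%, stage 1 alone would therefore use most of them, which is why the power statement should accompany the change.

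### Five replacements (38 in total) cover 13.2% non-evaluable drop-out, not the assumed 15-20%, so the stated 80% power is not what 38 enrolled subjects deliver on the plan's own assumption

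*Combined protocol and SAP*

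**What the plan says.** Everything on this point stands in section 8.3 (Sample Size).

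- The design is a Simon two-stage minimax design, "with a response probability of 20% or less to terminate the treatment and the hypothesized actual response probability of 40% or more", "at a significance level of 0.05 and a power of 0.8".
- Stage 1 takes 18 subjects. The futility rule at that point is: "the trial will be terminated by accepting the null hypothesis if 4 or fewer subjects respond to the treatment".
- If 5 or more respond, "then an additional 15 subjects will be accrued at the second stage", which makes 33. The drug is rejected at the end if 10 or fewer have responded, so 11 responders are needed.
- Enrolment is capped: "We intend to accrual a maximum of 38 subjects for this study".
- The cap is justified under the sub-heading on subjects who stop study drug before 16 weeks: "Based on the assumed drop-out rate of 15-20% and the goal of having 33 evaluable patients, 5 additional patients may be enrolled if needed".
- Under the same sub-heading, platelet counts are to be sought even after study drug is stopped. Only subjects who withdraw for a reason other than lack of efficacy or toxicity, and so have no platelet count, may be replaced. Everyone else is meant to be evaluable.

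Neither 8.3 nor 8.4 (Statistical Methods) gives a final cut-off for fewer than 33 evaluable subjects.

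**The concern.** The plan presents 5 replacements as following from 15-20% drop-out and a goal of 33 evaluable. Replacements also drop out, so the enrolment needed is 33 divided by (1 - drop-out rate), and 38 falls short of that at both ends of the range.

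The design has no slack to absorb a shortfall. Its power is almost exactly 80% at 33 evaluable subjects, and each subject lost while the cut-off stays at 11 responders lowers it. An active drug would then be rejected more often than the 20% that the plan implies. A reader faced with, say, 10 responders among 30 or 31 evaluable subjects would not know from the plan how much power that comparison had.

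**Working it through.** **Inputs, all from 8.3.** Response rates 0.20 (null) and 0.40 (alternative); 18 subjects in stage 1, continue with 5 or more responders; 33 in total, success with 11 or more; cap 38; drop-out 15-20%. The midpoint 17.5% is added here for illustration.

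**Step 1. Reproduce the design.** With n evaluable subjects and response rate p,

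P(success) = sum over x = 5 to 18 of P(Bin(18, p) = x) × P(Bin(n - 18, p) ≥ 11 - x).

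At n = 33 this gives 0.0458 at p = 0.20 and 0.801 at p = 0.40. A search over two-stage designs also returns 18/33 with these cut-offs as the minimax design. The 33-subject design is correct.

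**Step 2. What 5 replacements cover.** 5/38 = 13.2%.

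**Step 3. Enrolment needed for 33 evaluable on average, 33/(1 - d).**
- 15%: 33/0.85 = 38.8, so 39
- 17.5%: 33/0.825 = 40
- 20%: 33/0.80 = 41.25, so 42

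The shortcut 33 × d gives 4.95 at 15%, which matches the 5. At 20% even the shortcut gives 6.6. That the shortcut was used is an inference; the plan does not show its calculation.

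**Step 4. Chance of falling short with 38 enrolled.** Assume that drop-outs are independent, that each is non-evaluable, and that the trial reaches stage 2. Then P(fewer than 33 evaluable) = 1 - P(Bin(38, d) ≤ 5).

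**Step 5. Power and type I error.** By number evaluable, with the cut-offs as printed:

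| Evaluable | Power at p = 0.40 | Type I error at p = 0.20 |
|---|---|---|
| 33 | 80.1% | 0.046 |
| 32 | 77.2% | 0.038 |
| 31 | 73.8% | 0.031 |
| 30 | 69.7% | 0.025 |

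Averaged over the number of drop-outs D ~ Bin(38, d), with stage 1 filled to 18 evaluable and the final number evaluable = min(33, 38 - D):

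| Drop-out | Expected evaluable, 38(1 - d) | P(fewer than 33) | Power at p = 0.40 | Type I error |
|---|---|---|---|---|
| 15% | 32.3 | 51.5% | 75.7% | 0.037 |
| 17.5% | 31.4 | 67.5% | 72.9% | 0.033 |
| 20% | 30.4 | 80.0% | 69.4% | 0.028 |

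**Step 6. If only some drop-outs are non-evaluable.** The documents do not give this share, so the values below are assumptions. The non-evaluable rate is d × share.

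| Share non-evaluable | P(fewer than 33) at 15% / 20% | Power at 15% / 20% |
|---|---|---|
| All | 51.5% / 80.0% | 75.7% / 69.4% |
| Three quarters | 25% / 51% | 78.5% / 75.7% |
| Half | 6% / 17% | 79.8% / 79.1% |

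**The case against.** The strongest objection concerns what the 15-20% counts. It appears under a sub-heading about early discontinuation of study drug, and the same text says that counts will be sought after discontinuation and that most such subjects remain evaluable. If the rate means all early discontinuations, the shortfall shrinks and, at half non-evaluable, almost disappears. This stands as a limit on the size of the problem. It does not remove it: the sentence ties the rate directly to 33 evaluable subjects and to the 5 replacements, so the more natural reading is that it is the rate the replacements must cover. If another meaning was intended, the text needs to say so.

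A reader might infer that the trial is more likely than not to miss 33 evaluable subjects whatever the drop-out within the range. The figures do not support that at the low end. At 15% the gap is one subject and the chance of a miss is 51.5%, close to a coin flip. That figure is also conditional on reaching stage 2. At p = 0.40 the trial stops at stage 1 with probability 9.4%, so the chance of continuing and then falling short is 0.515 × 0.906 = 46.6%. At p = 0.20 it stops at stage 1 with probability 72%.

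A reader might also infer a risk of a false claim of activity. The opposite holds: keeping the cut-off of 11 with fewer subjects makes the test more conservative.

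Finally, this is a late amendment, and the sachet notes in 5.1 and 11.1 speak of enrolment in the past tense, so accrual may already be over. That would be a reason not to change the cap. The power statement would still matter for reading the result.

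**Conclusion.** The point holds in a limited form. As written, the sizing statement is arithmetically wrong: 5 replacements in 38 cover 13.2%, and the assumed 15-20% would call for 39 to 42 enrolled. The discrepancy is marginal at 15% and clear towards 20%.

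The consequence is lost power only, about 4 points at 15% (80.1% to 75.7%) and about 11 points at 20% (80.1% to 69.4%). At 20% the chance of rejecting a drug with a true 40% response rate is about 31%, against the planned 20%.

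These sizes rest on independent drop-out, all drop-outs being non-evaluable, stage 1 being filled to 18 evaluable, and the printed cut-offs being kept. The second assumption matters most. The two-stage design itself is sound at 33 evaluable subjects.

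**What to change.** In 8.3, keep the cap of 38 and the 15-20% assumption, and correct what is claimed for them. Suitable wording: *Five additional subjects allow for up to 13% non-evaluable drop-out (5/38). At the assumed 15-20%, about 30 to 32 evaluable subjects are expected from 38 enrolled, and power at a 40% response rate is then about 69-76% with the cut-off of 11 responders.*

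If the 15-20% was meant to count all early discontinuations, say so, and state the smaller non-evaluable rate that the 5 replacements are meant to cover.

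The assumed rate should not be lowered to 13% simply to fit the cap, because nothing in the documents supports a lower rate.

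The cost is one or two sentences and a less favourable power figure. No further enrolment or change to the decision rule is needed.

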8.4 Statistical Methods

The change of quality of life measure from baseline will be examined by the paired t-test or the Wilcoxon signed-rank. The planned analyses will include descriptive statistics on the proportions of responses (i.e. % subjects with treatment response) and the time to response. The response probabilities will be estimated using the sample proportions and their inferences including confidence intervals and hypothesis testing. Distributions of the sample proportions will be evaluated using Binomial distributions and their normal approximations.

The time to responses will be analyzed using appropriate tools in survival analysis, such as cumulative incidence estimate and Cox regression analysis for covariates, which takes consideration of both death without the event of interest as a complete risk and random censoring due to loss of follow-up. Graphical tools will be used to display the appropriate estimates (i.e. estimated proportions, the cumulative incidence curves, Kaplan-Meier curves) and their corresponding 95% confidence intervals. The Kaplan-Meier estimates and Cox regression will be used to evaluate the probability distributions of overall survival time.

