3.0 STUDY DESIGN

[figure not shown]
The study is designed as a non-randomized, Phase II, dose modification study of the oral TPO-R agonist eltrombopag in moderate aplastic anemia patients or those with bone marrow failure with unilineage cytopenia. The primary endpoint is measured at 16 to 20 weeks (+/- 7 days). Subjects with evidence for a clinical response in any lineage at 16 weeks but not yet meeting full primary endpoint response criteria, and who are tolerating investigational treatment, may receive an additional 4 weeks of eltrombopag and be reassessed after 20 weeks (+/- 7 days). At that time, if they meet primary endpoint response criteria, they will be eligible to enter the extended access part of the study. If they do not meet primary endpoint response criteria, eltrombopag will be discontinued. Subjects who cannot tolerate the medication or fail to respond by 16 to 20 weeks (+/- 7 days) will go off study. Drug dose during extended access will be at the lowest dosage that maintains stable blood counts or taken off drug for robust response until they meet off study

criteria or the study is closed. If subjects are taken off drug for robust response during extended access and maintain response, they will be taken off study after 3years.

Protocol Schema prior to January 8, 2015:

Protocol Schema after January 8, 2015:

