6.3 Monitoring during extended access

Patients fulfilling response criteria (per section 8.2) at the 16 or 20 week visit will be offered participation in the extended access cohort, and after signing consent will be permitted to continue on eltrombopag. Subjects taking eltrombopag must be evaluated at the Clinical Center every 6 months (+/- 30 days) while they remain on extended access and continue periodic laboratory monitoring in their home physician's office or the NIH every 2 weeks (+/- 7 days). Follow-up on this schedule will continue as long as they remain on eltrombopag on this clinical protocol.

Testing during NIH visit (every 6 months +/- 30 days) required for patients while on extended access and still being treated with eltrombopag:

- Acute care (Na, K, Cl, CO₂, Creatinine, Glucose, and Urea Nitrogen), Mineral (Phosphorus, Magnesium, Albumin, and Calcium), Hepatic (Alk Phosphatase, ALT, AST, Total Bilirubin, and Direct Bilirubin), and Other (Total Protein, CK, Uric Acid, and LDH) panel
- Bone marrow aspiration and core biopsy, to be stained for standard morphologic analysis and quantitation of cellularity with hematoxylin and eosin, and special stains to assess reticulin and collagen, primitive stem and progenitor cells via CD34 immunohistochemistry, and other lineage-specific or special stains as indicated to classify any abnormalities
- Bone marrow chromosomal analysis via standard cytogenetic techniques

- Flow cytometry of the peripheral blood to quantitate GPI-negative cells
- FACT questionnaire
- Iron panel (ferritin, transferrin, % saturation) at PI's discretion if indicated for iron metabolism and excretion studies
- 24 hour urine collection to determine the total iron content at PI's discretion if indicated for iron metabolism and excretion studies

On Study Monitoring every two weeks while on drug (+/- 7 days)

- Subjects may be followed by their home physician or at the Clinical Center. Progress notes and lab tests not done at the NIH will be faxed to the Research Nurse. The PI will review outside test results and these will be uploaded into CRIS and filed in the research charts, and all lab data will be recorded
- Complete blood counts with differential (every 2 weeks +/-7 days), Reticulocyte count
- ALT, AST, Total Bilirubin or Direct Bilirubin, (every two weeks +/- 7 days)

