6.4 Off study assessment

Patients who fail to respond to eltrombopag after 16 or 20 weeks (+/- 10 days) of therapy or who are taken off treatment prior to the 6 months evaluation for any of the other reasons listed in section 8.6 will likely choose to pursue other treatments, including immunosuppressive therapy, related, unrelated donor or cord blood transplantation, or experimental therapies. We will offer patients a follow-up evaluation at the NIH 6 months following being taken off eltrombopag treatment either due to lack of response or for the other reasons listed in section 8.6, but this visit will not be required. If they do not return to the NIH, we will contact their primary hematologist for information on their current hematologic status 6 months following their final dose of eltrombopag, and then take them off study.

If patients do return to the NIH at 6 months (+/- 30 days) for the off study assessment, the following may be performed, and then the patient will be taken off study:

- History and physical examination
- CBC with differential
- Acute care (Na, K, Cl, CO₂, Creatinine, Glucose, and Urea Nitrogen), Mineral (Phosphorus, Magnesium, Albumin, and Calcium), Hepatic (Alk Phosphatase, ALT, AST, Total Bilirubin, and Direct Bilirubin), and Other (Total Protein, CK, Uric Acid, and LDH) panel
- Reticulocyte count
- Peripheral blood smear
- Flow cytometry of the peripheral blood to quantitate GPI-negative cells
- Bone marrow biopsy with reticulin and collagen staining and aspiration with cytogenetics
- Lymphocyte phenotyping (TBNK flow cytometry)
- Research blood as detailed in section 7
- Iron panel (ferritin, transferrin, % saturation) at PI's discretion if indicated for iron metabolism and excretion studies
- 24 hour urine collection to determine the total iron content at PI's discretion if indicated for iron

General Quality of Life FACT questionnaire

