8.6 Off Study Criteria

8.6.1 Per Patient choice: Patients may withdraw from study at their request. The risks of withdrawing will be discussed, as will alternative treatment options. Those subjects who choose to withdraw while taking Eltrombopag will be strongly encouraged to continue to have labs monitored until he/she initiates alternative therapy.

8.6.2 Per principal investigator decision: Should any of the following adverse events occur during the 16 week study period, or in the extension treatment arm in responders, eltrombopag will be discontinued. The subject will be followed until resolution of the event. Labs will be monitored through 30 days off study drug time point or until he/she initiates alternative disease directed therapy at which time the subject's participation on this study will be considered complete and the subject will go off study.

- Intolerance of eltrombopag not resolved by dose reduction
- Life threatening acute hypersensitivity reaction
- Thrombosis/embolism (DVT, PE, stroke or TIA, myocardial infarction) other than central line thrombosis
- Persistent hepatotoxicity as defined in section 5.3.2
- New or worsening morphological abnormalities or cytopenia(s) as defined in section 5.4.2

- No treatment response after 16 to 20 weeks of treatment
- Any Grade IV toxicity considered related to the study medication excluding readily reversible metabolic or laboratory abnormalities or hematologic toxicities
- Significant progression of disease or a concomitant condition that would make the subject ineligible for further protocol participation
- Pregnancy or unwillingness to use acceptable forms of contraception
- Initiation of non-protocol therapy for aplastic anemia or bone marrow failure and unilineage cytopenia
- Cytogenetic abnormalities, new or worsening morphological abnormalities or cytopenia(s) as defined in section 5.4.2.
- Non-compliance with protocol procedures
- Lost to follow-up
- Study Completion

Once off study (either by per patient choice or per PI decision), subjects will be referred back to his or her referring physician or consented to the Hematology Branch evaluation and treatment protocol (94-H-0010) for consideration for standard therapy or evaluation for eligibility for another Branch protocol, depending on what is considered to be in the best interest of the subject.

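### Overall survival is planned by Kaplan-Meier and Cox although follow-up ends by outcome, so beyond about 6 to 10 months the curve describes responders only and may mislead if response predicts survival

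*Combined protocol and SAP*

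**What the plan says.** The survival analysis is one closing sentence of section 8.4: "The Kaplan-Meier estimates and Cox regression will be used to evaluate the probability distributions of overall survival time". The only censoring assumption in that section, "random censoring due to loss of follow-up", is stated for time to response, not for survival.

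Three sections describe when subjects without a response, or with toxicity or progression, leave follow-up, and they do not agree:

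- Section 3.0: "Subjects who cannot tolerate the medication or fail to respond by 16 to 20 weeks (+/- 7 days) will go off study".
- Section 8.6.2, which lists non-response, intolerance, thrombosis, hepatotoxicity, progression and cytogenetic change among its reasons: "Labs will be monitored through 30 days off study drug time point or until he/she initiates alternative disease directed therapy", after which participation ends.
- Section 6.4: a 6-month visit is offered, "but this visit will not be required". If the subject does not return, "we will contact their primary hematologist for information on their current hematologic status 6 months following their final dose of eltrombopag", and the subject then goes off study.

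For responders taking the drug, section 6.3 says: "Follow-up on this schedule will continue as long as they remain on eltrombopag on this clinical protocol". Responders who stop for a robust or stable response are followed for up to 3 years after the last dose (section 6.3.1). No section provides survival follow-up once a subject is off study, and section 9.2.3 collects serious adverse events only while the subject is on study.

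**The concern.** Kaplan-Meier and Cox treat a censored subject as having the same future risk as those still followed at that time. Here the protocol itself decides who is censored, mainly by non-response, toxicity or progression. If those outcomes carry a worse prognosis, the subjects who leave differ from those who stay, and the curve projects responders' later survival onto everyone treated.

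At stake is how any late survival figure would be read. It would look like survival of the treated cohort but would rest on a selected minority. A comparison of responders with non-responders from first dose would have two further faults: responders must survive long enough to be classified, and the groups are followed for very different times.

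**Working it through.** The plan gives no survival figure to reproduce, so the check asks how many subjects support the late curve and how far it could be off.

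**Inputs from the documents**

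- Evaluable subjects: 33; response rate 20% (null) and 40% (alternative), section 8.3.
- Response assessment at week 16 or 20, section 3.0.
- End of follow-up for non-responders, from the three sections above:
  - section 3.0: week 20, about 4.6 months;
  - section 8.6.2: week 20 plus 30 days = 170 days, about 5.6 months;
  - section 6.4: week 16 to 20 plus 6 months, about 9.7 to 10.6 months.

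**Subjects left once non-responders have gone**

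33 × 0.20 = 6.6 and 33 × 0.40 = 13.2, so about 7 to 13. This ignores deaths and responders' own later exits.

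**Inputs that are assumptions**

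- Constant yearly death rates h_r (responders) and h_n (non-responders). The documents give neither.
- A 3-year horizon, chosen for illustration; section 8.4 states none.
- All non-responders censored at t = 10/12 year, which gives the plan full credit for the section 6.4 contact.
- Proportion of responders π = 0.40.

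**Formulas** (large-sample limits)

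- S(t) = π·exp(−h_r·t) + (1−π)·exp(−h_n·t)
- True survival at 3 years: S(3)
- Kaplan-Meier limit at 3 years: S(10/12) × exp(−h_r × (3 − 10/12))

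**Worked case, 2% and 10%**

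- True: 0.4·exp(−0.06) + 0.6·exp(−0.30) = 0.3767 + 0.4445 = 0.821.
- Kaplan-Meier: S(10/12) = 0.9454; exp(−0.02 × 2.1667) = 0.9576; product 0.905.

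| Yearly death rate, responders / non-responders | True 3-year survival | Kaplan-Meier | Difference |
|---|---|---|---|
| 2% / 2% | 94.2% | 94.2% | 0 |
| 2% / 5% | 89.3% | 92.8% | 3.5 points |
| 2% / 10% | 82.1% | 90.5% | 8.4 points |
| 3% / 15% | 74.8% | 86.2% | 11.4 points |

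**Sensitivity, 2% / 10% case**

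- Censoring at week 20 (section 3.0 read literally): S(20/52) × exp(−0.02 × (3 − 20/52)) = 0.9743 × 0.9490 = 92.5%, against the same true 82.1%. Which exit rule applies therefore changes the answer.
- π = 0.20, censoring at 10 months: true 78.1%, Kaplan-Meier 0.9327 × 0.9576 = 89.3%.

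**The case against.** The strongest reply is that this hardly matters. Overall survival appears in no objective and no endpoint (sections 1.0, 8.1, 8.2). The go/no-go decision rests on response counts, and safety stopping rests on treatment-related events. All of that stands, and it sets the severity.

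The second reply is that the bias is not shown. This also stands. A reader might infer that the planned analysis overstates survival as a matter of fact; the documents do not support that. Section 2.2 describes causes of death among non-responders to immunosuppression, not death rates by response to eltrombopag. Section 6.4 expects non-responders to go on to other treatment, including immunosuppression or transplantation. The direction is plausible, but the size is assumed, and it is zero if the death rates are equal.

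Two other inferences should be resisted:

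- That the late risk set consists only of subjects taking the drug. Responders who have stopped it are followed too.
- That section 8.4 plans a Cox comparison of survival by response. It names no covariates for the survival model; covariates are mentioned for time to response.

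None of this removes the core point. The censoring is prescribed by outcome, and the plan neither says so nor limits the estimate accordingly.

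**Conclusion.** The concern holds in a conditional form. As planned, the survival curve beyond about 6 to 10 months describes responders, on or off drug, and not the treated cohort; that follows from the follow-up rules alone. Whether it overstates cohort survival depends on response predicting survival, which the documents do not establish. In the unequal-rate scenarios with 40% responders and censoring at 10 months, the 3-year overstatement is about 3 to 11 points; with equal rates it is nil.

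Severity is low, because the primary analysis, the sample size and the stopping rules do not depend on overall survival. The change is still worth making because it is cheap.

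**What to change.** 1. In section 8.4, limit the all-subject survival estimate to 6 months from first dose. The section 6.4 contact falls 6 months after the last dose, so its due date is never earlier than this horizon, even for a subject who stops early. Subjects who withdraw consent or are lost remain censored and should be counted.
2. In section 6.4, record vital status and its date at that contact; at present only hematologic status is requested. Because the visit has a window of 30 days either side, ascertain vital status at or after 6 months from first dose.
3. Report later survival separately and descriptively for extended-access responders, with time zero at entry to extended access. Do not enter response as a baseline covariate in a Cox model that starts at first dose.
4. Reconcile sections 3.0, 6.4 and 8.6.2 on when follow-up ends. Step 1 depends on the section 6.4 contact applying to everyone who leaves.

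The cost is a few sentences in section 8.4, one data item at a contact already planned, and the wording of three sections. The downside is that no long-term survival figure is given for the whole cohort, which the planned follow-up cannot support.
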